4.1 Inclusion Criteria

SLOS subjects with the following characteristics will be enrolled:

- 1. Ages 2-28 years at enrollment.
- 2. Subjects (or their parents/legally-authorized representative) must provide signed informed consent.
- 3. Assent must be obtained from those subjects ages 7-17 years (or 7-18 years, for some STAIR sites) who are intellectually capable of understanding this study.
- 4. Diagnosis of SLOS based on clinical features and biochemical/genetic confirmation.
- 5. Subjects are capable of traveling to the STAIR study site.
- 6. Fasting serum cholesterol ≤125 mg/dL within the prior 6 months must be established before enrolling in the study. This level of cholesterol will be confirmed at the first STAIR visit prior to starting cholic acid therapy.
- 7. Clinically stable at the time of enrollment (see below for definition of clinical conditions which would preclude enrollment)
- 8. Subjects must be on a constant dietary cholesterol intake for at least 3-months prior to treatment with cholic acid.

- 9. Subjects must agree to make no changes in cholesterol supplementation during the STAIR study.
- 10. SLOS subjects who are taking antioxidants or drugs for neurologic/psychiatric symptoms may be included if they agree to make no changes in the medication dose during this study.
- 11. Subjects must have internet access and computer (or tablet, smart phone) to allow telehealth visits and/or observation of drug preparation.

4.2 Exclusion Criteria

Subjects with the following characteristics are excluded from this study:

- 1. Subject has an unstable clinical condition that, in the judgment of the principal investigator, would prevent completion of the study. Medically unstable patients would include those patients with severe liver disease, those patients with complex birth defects such as severe heart disease or renal dysplasia, those patients with severe respiratory compromise requiring tracheostomy, or patients not likely to survive longer than 1 year.
- 2. Subject has transaminase elevations (>3-fold above the reference range) at baseline.
- 3. Subject is taking drugs (statins, bile acid sequestrants, ezetimibe) or nutraceuticals (red yeast rice, phytosterols, polycosanol, high dose omega-3 fatty acids) that are known or suspected to lower serum cholesterol levels.
- 4. Subject is pregnant.

4.3 Recruitment of Participants

SLOS subjects will be recruited from each of the STAIR sites listed in Participating Institutions/Investigators. Most subjects will be already known to the site PIs and followed in their centers. We will also recruit subjects with the assistance of the Smith-Lemli-Opitz/RSH Foundation and their website, and families will be notified of this study at the annual SLOS Foundation Family Conference. The study will be posted on www.clinicaltrials.gov. Finally, we may advertise the study to medical geneticists at the national meetings of the American Society of Human Genetics and American College of Medical Genetics.

4.4 Retention Strategies

Retention of subjects in the study will be encouraged by conducting weekly telephone calls and promptly addressing any issues, complications or adverse events that may arise. Also, to encourage retention, efforts will be made to reimburse costs for travel expenses and hotel accommodations for subjects for their STAIR site visits.

4.5 Data Elements

Every individual who provides consent will be assigned a unique numerical identifier that will ensure anonymity throughout the study. Study personnel at each STAIR site who interact with the subject will know them by name and have access to their HIPAA identifiable data, however this information will not be shared with the entire study personnel group. Each STAIR site that enrolls subjects will upload anonymous subject data into a REDCap database that is maintained by the DMCC.

4.6 Schedule of Events

The schedule of event for this study is shown in the Table 1.

Table 1: Schedule of Events

				Post-
Phase:		Treatment		Treatment
Visit Site:	STAIR	Local (or	STAIR	Local (or
		STAIR)		STAIR)
Timepoint:	Week	Week 4**	Week 8	Week 12
	0 Baseline			
Assessment		± 5 days	± 5 days	± 5 days
Eligibility and	X			
Written Consent				
Demographics	Х			
Physical Exam	X		Х	
Medical History	Х			
Concomitant	Х	X	X	X
Medications				
STAIR Site Labs/Local Labs*	Х	X	X	X
Dietary History	Х	Х	Х	X
Teaching and	X			
observation of				
drug preparation				
Pregnancy Test	X		X	
Weekly phone	Inquire about	t AEs, dietary hi		ngs, change in
calls	medications, etc.			
Adverse Events	Will be included in weekly phone calls.			
Reporting				
Patient-Reported	This data will be collected daily and analyzed weekly			
Dietary History	20.1	U OTAID II		1

^{*} These labs will be drawn at the STAIR site or locally for subjects.

5.0 Data and Safety Monitoring Plan

The study protocol will be reviewed and approved by the NIH before submission to the STAIR IRB of Record for approval. Participant enrollment may only begin with IRB approved consent forms.

Adverse events (AEs) will be recorded from each subject on a weekly basis by the local clinic coordinators at each study site. This will be done at routinely scheduled weekly telephone calls and include all contact initiated by the subjects themselves. AEs will include medical illnesses, change in medical condition, suspected side effects of cholic acid, complications of phlebotomy, etc. AEs will be reported to the Study Chair who will review them weekly. The Medical Review Officer and Study Chair, together with input

^{**} Note that weeks 4, 8 and 12 refer to time after the start of cholic acid therapy.

from the study site PIs, will decide whether AEs rise to the level of seriousness or unusual character or frequency as to suspend the study.

In addition, this study will be reviewed every 6 months by the UNMC Data Safety Monitoring Board (DSMB) for safety concerns, complicating issues, and study progress.

5.1 Study Oversight

The Study Chair ([name] [name]) has primary oversight responsibility of this clinical trial. The UNMC appointed Data Safety Monitoring Board (DSMB) has oversight responsibility of the Data Safety Monitoring Plan (DSMP) for this clinical trial. The DSMB will review accrual, patterns and frequencies of all adverse events, and protocol compliance every 6 months. The DSMB makes recommendations to the NIH regarding the continuation status of the protocol.

Each site's Principal Investigator and their research team (co-Investigators, research nurses, clinical trial coordinators) are responsible for identifying adverse events. Aggregate report detailed by severity, attribution (expected or unexpected), and relationship to the study drug/study procedures – will be available from the DMCC for site review. Adverse events will be reviewed monthly by the research team. A separate report detailing protocol compliance will also be available from the DMCC for site review on a monthly basis. The research team will then evaluate whether the protocol or informed consent document requires revision based on the reports.

5.2 Definitions and Standards

An adverse event is defined as: "...an unfavorable and unintended sign, symptom or disease associated with a participant's participation in a study."

Serious adverse events include those events that: "result in death; are life-threatening; require inpatient hospitalization or prolongation of existing hospitalization; create persistent or significant disability/incapacity, or a congenital anomaly/birth defects."

An unexpected adverse event is defined as any adverse experience...the specificity or severity of which is not consistent with the risks of information described in the protocol.

Expected adverse events are those that are identified in the research protocol as having been previously associated with or having the potential to arise as a consequence of participation in the study

All reported adverse events will be classified using the current version of the Common Terminology Criteria for Adverse Events (CTCAE) developed and maintained by CTEP at National Cancer Institute.

5.3 Expected/Known Risks/Discomforts/Adverse Events Associated with Study Intervention and Procedures: Definition of Expected Adverse Events

The risks of cholic acid therapy in SLOS are expected to be low, in part due to the endogenous nature of cholic acid which is normally made in the liver and excreted into the intestine. Based on the 3 studies in patients with single enzyme defects (SED) of bile acid synthesis and Zellweger syndrome spectrum disorders (ZSD), diarrhea was identified as the most frequent AE, occurring in 2% of this population. In addition, the following AEs were noted at frequencies of 1% or less: reflux esophagitis, malaise, jaundice, nausea, abdominal pain, intestinal polyp, skin lesions, urinary tract infections and peripheral neuropathy. In this population, cholestasis and liver dysfunction was seen in 58/79 (86% of patients). Five patients exhibited worsening liver function on cholic acid. Five additional patients without liver dysfunction at the time of cholic acid initiation developed liver dysfunction on the drug. In contrast to SED and ZSD, SLOS is not usually associated with liver disease, although some SLOS subjects do have mildly elevated serum transaminases. Consequently, it is not expected that cholic acid therapy will lead to liver related AEs. Nevertheless, safety monitoring for worsening of the liver will be done at least monthly and more frequently if clinically indicated.

Risks of Phlebotomy:

- Procedure and risks: In general, phlebotomy is considered to carry a very low risk of
 complications. Venous blood is typically removed from an accessible site such as the
 arm using a small needle. Blood drawing will cause some mild temporary pain and
 carries a small risk of bleeding, bruising and/or infection at the puncture site.
- Protections from risk: To decrease discomfort of the needle poke in children, we will use topical anesthetic EMLA cream applied to the skin 30 minutes in advance of the procedure. To minimize associated risks of bleeding and bruising, only experienced phlebotomists will draw blood for our studies. Bleeding and bruising at the puncture site is usually easily controlled with the application of direct pressure and a bandage. Bruising at the puncture site is occasionally seen, but is not harmful. Using standard phlebotomy procedures with sterilization of the skin and gloved personnel, infection from routine venous phlebotomy is exceedingly rare. It can be treated effectively with antibiotics, if necessary. The minimal amount of blood necessary to carry out our STAIR studies will be collected. We will not exceed 7 ml of blood/kg body weight per 6 weeks, which is considered safe in children and will not cause anemia or related symptoms.

5.4 Reporting Timeline

- Within 24 hours of learning of any Serious Adverse Event (SAE), investigators must report it to the study PI and DSMB if it:
 - Is considered life-threatening/disabling or results in death of subject
 OR-
 - Is Unexpected/Unanticipated
- Investigators must report all other reportable SAEs within **5 working days** (of learning of the event).

 All other (suspected) reportable AEs must be reported to the DSMB within 20 working days of the notification of the event or of the site becoming aware of the event.

5.5 RDCRN Adverse Event Data Management System

Upon entry of a serious adverse event, the DMCC Data Management system will immediately notify the Study Chair, site Pls, and any additional agencies (if applicableindustry sponsor, CTEP, etc) of any reported adverse events via email.

Serious adverse events: The Medical Review Officer (MRO) determines causality (definitely not related, probably not related, possibly related, probably related, definitely related) of the adverse event. The MRO [and Retrophin] may request further information if necessary and possibly request changes to the protocol or consent form as a consequence of the adverse event. A back-up notification system is in place so that any delays in review by the MRO beyond a specified period of time are forwarded to a secondary reviewer. The DMCC REDCap system maintains audit trails and stores data (and data updated) and communication related to any adverse event in the study.

Non-serious expected adverse events: Except those listed above as immediately reportable, non-serious expected adverse events that are reported to or observed by the investigator or a member of his/her research team will be submitted to the DMCC in a timely fashion (within 20 working days). The events will be presented in tabular form and given to the MRO and UNMC DSMB on a bi-annual basis. Local site investigators are also required to fulfill all reporting requirements of their local institutions.

The DMCC will post aggregate reports of all reported adverse events for site investigators.

5.6 Study Discontinuation

The NIH and local IRBs (at their local site) have the authority to stop or suspend this trial at any time. This study may be suspended or closed if:

- Early stopping rules have been met.
- Accrual has been met.
- The study objectives have been met.
- The Study Chair / Study Investigators believe it is not safe for the study to continue.
- The DSMB recommends suspending or closing the trial
- The NIH suspends or closes the trial.
- The FDA suspends approval of Cholbam for human use.
- Retrophin withdraws use of Cholbam.

Premature discontinuation of this study will also occur under the following circumstances:

• Adverse events (AEs) are determined to occur in a significant proportion of subjects or the AEs are serious enough that the subjects are judged to be at high medical risk if participation in the study continues. An adverse event would include hospitalization, or marked worsening liver function or GI symptoms severe enough to prevent the patient from taking the cholic acid.

Failure to retain subjects and complete the study.

The study involves treating SLOS subjects with cholic acid. For this purpose, AEs will be reviewed by the Medical Review Officer and DSMB to determine if the AE is related to the drug.

5.7 Subject Withdrawal and/or Cholic Acid Dose Interuption/Reduction

The following conditions will result in withdrawal of the subject from the study:

- Withdrawal of consent
- Withdrawal by the participant
- Withdrawal by the investigator
- Intercurrent illness or event that precludes further visits to the study site or ability to evaluate disease (e.g.-mental status change, serious illness, pregnancy).

Withdrawal from the study will be permitted at any time with the agreement of the Principal Investigator and/or SLOS subject (or parent/legal authorized representative). Withdrawal may be necessitated for clear evidence of non-compliance, adverse effects of the drug, onset of concurrent illness, or new SLOS complication that prevents continuation. All data acquired prior to termination for the reasons outlined below will be included in the primary analysis unless the subject provides a written request to delete all of their data from the data base and subsequent analyses. Every effort will be made to conduct a final study visit with the participant and participants will be followed clinically until, if applicable, all adverse events resolve.

Cholic Acid Dose Reduction

- 1. During the Treatment Phase, administration of cholic acid may be interrupted for up to 3 successive days if the subject develops an acute illness and cannot tolerate the drug, for example due to vomiting or diarrhea. Interruption of drug for a longer period of time (>5 days) may trigger withdrawal from the study, upon review and agreement by the Principal Investigator and site investigators or the Medical Review Officer.
- 2. In addition to a temporary complete interruption of cholic acid administration, evidence of worsening liver function may prompt a reduction in drug dosage. Worsening of liver function is defined as:
 - AST, ALT and/or GGT >3 times above baseline measurements or >300 IU in any patient and/or
 - A total bilirubin value >3 mg/dL (if the baseline level is <10) and/or
 - onset of serious gastrointestinal symptoms not clearly associated with a limited infectious illness

Worsening of liver function will trigger a review by the Prinicipal Investigator and reduction of cholic acid dosage to 5 mg/kg/day. Monitoring labs will be obtained 1 week after lowering the dose. If the subject does not tolerate this lower dose, based on symptoms or persistently abnormal test results, the subject may be withdrawn from the study.

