5.9 Quality Control: Study Related Procedures

Study related procedures will be outlined in a Manual of Operations (MOO), which will be distributed to each of the study sites. The MOO will include descriptions of methods for blood collection, processing and storage. Instructions will be included for shipment of specimens to the Study Chair for batch shipment to reference laboratories for testing.

6. Statistical Considerations

Data from this study will be submitted to the DMCC located at the Cincinnati Children's Hospital & Medical Center. Physical examination, laboratory studies, vital signs, and growth parameters assessed at week 0 and week 8 will be tabulated. The difference in total serum cholesterol, 7-DHC and 8-DHC, sterol ratio, oxysterol levels, serum bile acids, and liver function from the baseline visit (week 0) to week 8 visit will be calculated for each participant. The average change and 95% confidence intervals for each of these measurements will be estimated.

Safety data will be summarized for all treated subjects using appropriate tabulations, and descriptive statistics. The incidence rate of each adverse event will be estimated and reported with exact 95% confidence intervals.

Sample size: This pilot study is intended to explore preliminary signals for efficacy as well as examine safety of cholic acid supplementation. The primary purpose of the study is to detect a difference in pre-and-post treatment mean serum cholesterol level of one group. The sample size was based upon a sufficient number of participants to begin such explorations prior to pursuit of a randomized controlled trial and historical variation in serial serum cholesterol levels in SLOS subjects. We conservatively use the population effect size of 0.80 and the significance level (alpha) of 0.05 using a two-sided one-sample t-test. With an accrual of 13 evaluable participants, an estimated standard deviation of 5 mg/dl with mean 61 mg/dl for the cholesterol measurements, a within subject correlation of .8 (between pre and post testing) and a two-sided alpha of 0.05, there is greater than 80% power to detect a change in total serum cholesterol of greater than 10 mg/dl. Under the same assumptions, for sterol ratio of 7-DHC/cholesterol, based on a standard

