7.4 Study Records Retention

Hard copies of data forms will be stored at each STAIR study site that enrolls subjects. Forms will be stored for at least 5 years after completion of the study.

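### Section 5.7 lets a withdrawing subject delete all data, with no safety exception; if a treated subject does so, the Section 6 adverse event summary of every treated subject cannot be delivered

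*Combined protocol and SAP*

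**What the plan says.** Section 5.7 sets a default and an exception in one sentence. The default is "All data acquired prior to termination for the reasons outlined below will be included in the primary analysis". The exception is "unless the subject provides a written request to delete all of their data from the data base and subsequent analyses". It covers all data and does not set adverse events, liver tests or dosing records apart. The sentence before it reads in part "Withdrawal may be necessitated for clear evidence of non-compliance, adverse effects of the drug", so subjects who leave because of harm are among those who may use the exception.

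Section 6 (Statistical Considerations) says "Safety data will be summarized for all treated subjects using appropriate tabulations, and descriptive statistics" and then "The incidence rate of each adverse event will be estimated and reported with exact 95% confidence intervals". It does not mention deleted subjects. Section 4, under Study Outcome Measures, names adverse event incidence as the second primary outcome measure, and the synopsis also lists it as primary.

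**The concern.** A safety summary of every treated subject has a fixed denominator: everyone who took a dose. Section 5.7 allows that denominator to shrink after the fact, at the request of someone whose outcome is already known to them. Anyone applying both sections after such a request must break one of them, and the plan does not say which gives way.

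At stake is one of the two primary outcome measures, in a trial of at most 15 subjects, for a drug that the synopsis says has no defined safety profile in this disease. One deletion can remove an event type from the table altogether and also lower the upper confidence limit, so the result would look both cleaner and better bounded. The plan does not require deletion requests to be counted or reported, so a reader of the results might have no means of seeing the gap.

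**Working it through.** **The two rules side by side.** After a written request from a subject who took at least one dose:

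- Section 5.7: the subject's data leave the database and all later analyses.
- Section 6: the subject belongs in the safety summary, because the subject was treated.

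No reading of the two satisfies both. Without a request there is no conflict.

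**Inputs.**

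- Maximum number treated: 15 (synopsis and Section 6). Section 6 derives this from 13 evaluable subjects and 15% dropout. 13 × 1.15 = 14.95 gives the stated 15. Dividing instead, 13 / 0.85 = 15.3, gives 16. The stated 15 is used here as the ceiling.
- Interval method: exact 95%, as Section 6 specifies, taken as Clopper-Pearson. Lower limit = 2.5% quantile of Beta(x, n − x + 1); upper limit = 97.5% quantile of Beta(x + 1, n − x). For x = 0 the upper limit is 1 − 0.025^(1/n).
- Event counts: **assumed**, since the documents give none. I show 1, 2 and 3 affected subjects.

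**An affected subject asks for deletion.** The proportion goes from x/n to (x − 1)/(n − 1), a fall of (n − x)/[n(n − 1)].

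| All treated subjects kept | After one deletion | Fall in percentage points |
|---|---|---|
| 1/15 = 6.7% (0.2% to 31.9%) | 0/14 = 0% (0% to 23.2%) | 14/210 = 6.7 |
| 2/15 = 13.3% (1.7% to 40.5%) | 1/14 = 7.1% (0.2% to 33.9%) | 13/210 = 6.2 |
| 3/15 = 20.0% (4.3% to 48.1%) | 2/14 = 14.3% (1.8% to 42.8%) | 12/210 = 5.7 |

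In the first row the upper limit falls from 31.95% to 23.16%, about 8.8 points. If both affected subjects in the second row ask, 2/15 becomes 0/13 (0%, upper limit 24.7%).

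**An unaffected subject asks.** The proportion goes from x/n to x/(n − 1), a rise of x/[n(n − 1)]. So 1/15 becomes 1/14 (6.7% to 7.1%, a rise of 0.5 points), and 2/15 becomes 2/14 (13.3% to 14.3%, a rise of 1.0 point). The direction of the error depends on who asks, and the two errors are not of equal size: losing an affected subject moves the estimate far more.

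**The case against.** **Safety oversight does not depend on the final table.** This stands. The Study Chair reviews adverse events weekly (Section 5.0). Serious events are reported within 24 hours or 5 working days, and other reportable events go to the DSMB within 20 working days (Section 5.4). Tables of non-serious expected events go to the Medical Review Officer and DSMB twice a year (Section 5.5). A reader might infer that deletion wipes an event from the trial's knowledge. The documents do not support that: the clause reaches later analyses and does not recall reports already made. But those reports do not put the subject back into the primary outcome table.

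**Records retention.** A reader might also see a conflict with Section 5.5, where the data system "stores data (and data updated) and communication related to any adverse event in the study", or with Section 7.4: "Forms will be stored for at least 5 years after completion of the study". Neither is a contradiction. Section 5.5 also provides for audit trails, and an audit trail can record a deletion. Section 7.4 concerns paper forms at the sites, which can be kept while database entries are removed.

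**Unassayed specimens.** Research sterol specimens are frozen and tested in batches, so a reader might infer that samples drawn before withdrawal but not yet assayed are excluded. Section 5.7 does not say so, and silence is not exclusion. It would not touch the safety tests in any case, because these are run at once.

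**Who asks for deletion.** It is tempting to say that families who leave because of harm ask more often. The documents show only that harm can lead to withdrawal. The further step is an assumption.

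**Size.** The counts are hypothetical, the paired intervals overlap widely, the safety analysis is descriptive, and the plan sets no numerical event rate that one deletion would cross. All of this is true. It limits the consequence but does not reconcile the two sections.

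**Conclusion.** The concern holds in a narrow, conditional form. If a treated subject uses the deletion clause, Sections 5.7 and 6 cannot both be followed, and the incidence table for the second primary outcome measure loses that subject from numerator and denominator. With 15 treated subjects and an affected subject asking, the estimate falls by about 6 to 7 percentage points for one to three affected subjects, and a single event disappears from the table.

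The conflict in the text needs no assumption beyond a request being made. The figures assume 15 treated subjects and the event counts shown. A systematic downward bias would need the further assumption that affected subjects are more likely to ask. How often requests would occur cannot be judged from the documents. The point is confined to the safety analysis; it is not a claim that events would escape oversight or that record-keeping rules are broken. It is worth correcting because the rule is explicit, the sample is very small and the repair is cheap.

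**What to change.** Rewrite the exception in Section 5.7 so that it agrees with Section 6:

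- Withdrawal stops further research data collection. The existing provision in Section 5.7 for a final visit and for following unresolved adverse events is left as it is.
- Exposure and safety data collected up to withdrawal are retained.
- Every subject who took at least one dose stays in the safety summary.

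If the sponsor wishes to keep some deletion option, for example for stored untested specimens or for non-safety research data, Section 6 should require the number of requests and the resulting denominators to be reported. Check that the consent wording agrees. The consent form is not in the material available here, so this is a check and not an alleged error.

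The cost is a sentence or two in Section 5.7, a matching line in Section 6, and possibly a consent edit. The small downside is that families lose the option to remove coded safety data already collected. They can still leave the study at any time.
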